3.2.2. Primary Endpoint - Effectiveness

Complete Occlusion:

Rate of complete aneurysm occlusion (Raymond I) without significant parent artery stenosis ($> 50\%$ stenosis) or prior retreatment at 1 year post-procedure.

The aneurysm occlusion and parent artery stenosis assessments in this endpoint will be evaluated by the independent core laboratory. Retreatment will be reported by the site.

Figure 3.2.2A Raymond Scale [Roy 2001]

- **Class I: Complete** = Complete obliteration
- **Class II: Residual Neck** = Persistence of any portion of the original defect of the arterial wall but without opacification of the aneurysmal sac
- **Class III: Residual Aneurysm** = any opacification of the aneurysm sac

3.2.3. Secondary Endpoints - Effectiveness

The secondary effectiveness endpoints are pre-specified below and have been identified as outcomes meaningful to evaluate the effectiveness of aneurysm treatment with a device that is an adjunct to embolic coiling.

- Technical Success is defined as successful implantation of device— physician able to access target aneurysm, deploy PulseRider device at the neck of aneurysm and device was detached successfully. This endpoint will be reported by the investigator.
- Ability to retain embolic coils within aneurysm immediately post-procedure. This endpoint will be evaluated by the independent core laboratory.
- Complete aneurysm occlusion at 3 years and 5 years.
- Adequate aneurysm occlusion (defined as Raymond I and II combined) at 1 year, 3 years and 5 years.
- The percentage of target aneurysms that are retreated through 1 year, 3 years and 5 years. Retreatment will be reported by the investigator.
- The percentage of subjects with significant stenosis defined as $> 50\%$ at implant site at 1 year, 3 years and 5 years. This endpoint will be evaluated by the independent core laboratory.
- The percentage of subjects with mRS 0 – 2 at 1 year, 3 years and 5 years.

3.2.4. Additional Endpoints

- The percentage of target aneurysm rupture up to 1 year, 3 years and 5 years. This endpoint will be evaluated by the independent core laboratory.
- No migration (defined as $\leq 2\text{mm}$) of the device at 1 year, 3 years and 5 years. This endpoint will be evaluated by the independent core laboratory.

4. Study Population

4.1. Participant Inclusion Criteria

Investigators will assess potential subjects who are candidates for the study. In addition, an image of the subject's aneurysm and branch arteries must be reviewed and approved by the Image Screening Committee. Candidates who meet the protocol inclusion/exclusion criteria with at least one bifurcation intracranial aneurysm that is acceptable for minimally invasive treatment and approved by the Image Screening Committee may be enrolled. The subject selection criteria are in place for protection of participants and to address factors that may compromise the outcome of the investigation or interpretation of the results.

Candidates for this study must meet ALL of the following criteria:

1. Subject with an angiographically confirmed digital subtraction angiogram (DSA) or computed tomography angiogram (CTA) of wide neck (≥ 4 mm or dome to neck ratio < 2) intracranial aneurysm located at a bifurcation of the basilar artery, carotid terminus, MCA or ACOM
2. The parent vessel for the target aneurysm has a diameter of 2.0 mm to 4.5 mm
3. The subject is between 18 and 80 years of age the time of consent
4. Informed consent is obtained and the subject signs the Institutional Review Board (IRB) approved consent prior to beginning any study procedures along with the HIPAA Authorization for the release of PHI
5. In the opinion of the treating physician, placement of the PulseRider device is technically feasible and clinically indicated
6. Subject has the mental capacity, willingness and ability to comply with protocol requirements and follow-up through 5 years for the clinical study

4.2. Participant Exclusion Criteria

Candidates will be excluded from participation if ANY of the following apply:

1. Unstable neurological deficit (condition worsening within the last 90 days)
2. Subarachnoid Hemorrhage within the last 60 days
3. Irreversible bleeding disorder
4. Modified Rankin Score (mRS) score ≥ 3
5. Patient has another intracranial aneurysm that in the Investigator's opinion, may require treatment within the 1 year follow up period
6. Patient has previously had two or more (≥ 2) procedures to treat the target aneurysm
7. Patient with an untreated target aneurysm that is partially thrombosed
8. Platelet count $< 100 \times 10^3$ cells/mm³
9. Inability to tolerate, adverse reaction to or any contraindication to taking aspirin or P2Y12 inhibitor

10. A history of contrast allergy that cannot be medically controlled
11. Known allergy to nickel
12. Relative contraindication to angiography (e.g., serum creatinine > 2.5 mg/dL)
13. Woman of child-bearing potential who cannot provide a negative pregnancy test
14. Evidence of active systemic infection (e.g. fever with temperature > 38°C/100.4°F and/or white blood count (WBC) > 15,000)
15. Conditions that carry a high risk of neurological events or stroke (e.g., uncontrolled hypertension, prior ischemic stroke, Moya moyo disease).
16. Evidence of disease or condition expected to compromise survival or ability to complete follow-up assessments during the 5 year follow-up period
17. Vessel tortuosity or stenosis that prohibits safe endovascular access to the target aneurysm to allow for treatment with the study device
18. Current involvement in a study for another investigational product
19. Patient and /or family considering a move from this geographical location at the time of consent
20. Categorized as a vulnerable population and require special treatment with respect to safeguards of well-being (e.g. cognitively impaired, veteran, prisoner, etc.)

4.3. Strategies for Recruitment and Retention

The study will enroll a total of 160 subjects in the United States at up to 28 clinical sites. Once enrolled, each subject will participate in the study for 5 years post-procedure. A recruitment packet, that can be customized, may be provided to each clinical site. The packet may include a sample email/letter to referring physicians, a slide deck explaining the clinical study for presentation at grand rounds or other meeting of referring physicians and a patient information booklet describing the device, the indications, the clinical study and the necessary commitment to completing all study visits.

The Sponsor's intention is for the enrolled subject population to be as representative as possible of the well-defined study population. Investigators will be encouraged to evaluate all unruptured and bifurcation aneurysm patients for participation in the study, and to offer enrollment to all who meet preliminary eligibility criteria.

Clinical sites will be selected for participation in the study based on experience with similar stenting technologies, ample unruptured bifurcation aneurysm patient population, the capacity to screen and enroll a reasonable number of eligible patients, and the ability to perform the required study procedures, per this protocol. Sponsor will attempt to include a diversified group of investigational sites engaging a variety of academic and private institutions geographically located throughout the US. To ensure generalizability of results and minimize the influence of any single site, no more than approximately 20% of the total

enrollment will be allowed at a single site (i.e., a maximum of 32 subjects enrolled per site).

In order to enhance participant retention and compliant follow-up visits, site coordinators will be encouraged to schedule their subject follow-up visits early in the visit windows with ample opportunity to reschedule as needed, before the visit window closes.

4.4. Participant Withdrawal or Termination

4.4.1. Reasons for Withdrawal or Termination

Subjects are free to withdraw from participation in the study at any time upon request. The investigator may terminate participation in the study if any adverse event or other medical condition or situation occurs such that continued participation would not be in the best interest of the participant. A subject may be terminated if they meet an exclusion criterion (either newly developed or not previously recognized) that precludes further study participation.

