4.4.2. Handling of Participant Withdrawals or Termination

Subjects that withdraw consent after treatment are not required to undergo follow-up after withdrawal. They will not be replaced and will be considered part of the subject cohort. The reason for early withdrawal will be documented in the source documents and case report forms.

In the event a subject withdraws from the study, their data will be excluded from the data analysis from the time of withdrawal going forward. All data collected prior to withdrawal will be included in the data analysis.

5. Study Device

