10.3.4. Primary Endpoint Analyses

Primary Safety Endpoint

The primary safety endpoint analysis will be conducted on the mITT analysis set.

If a subject experienced a death due to neurological causes or a major ipsilateral stroke in downstream territory within a year post-procedure then subject will be deemed a failure on the endpoint. If a subject completed the 1 year follow up and did not experience any such event then subject will be deemed a success on the endpoint. If a subject did not complete the 1 year follow up and did not experience such event then the subject will be imputed with a multiple imputation method that will make use of the similarities between the subject's demographic, procedural, and aneurysm characteristics with those of the subjects with a non-missing endpoint (those who either experienced an event and those who completed the study without experiencing an event). The imputation method will also account for the length of time between the procedure and the last time the subject was seen. The longer that time period is, the less likely the subject will be imputed with an event.

Subjects for whom implantation of the PulseRider was attempted but not successful will be followed up to a year. Any safety events which occur due to attempted implant or from retreatment, and which meet the primary safety endpoint definition will count as failures in the analysis. If such a subject is lost to follow-up then subject will be imputed with data based on other subjects for whom the implantation was not successful but who were not lost to follow-up.

The multiple imputation method results in a large collection of imputed datasets. The proportion of primary endpoint events and its variance is computed for each dataset. Within and between imputation variances are then combined according to Rubin's method [Rubin 1996] in order to produce a single variance estimate for the proportion of events.

The endpoint will be considered successful if the upper bound of the 2-sided 95% normal approximation based confidence interval for the rate of events is less than a performance goal of 15%.

Primary Effectiveness Endpoint

The primary effectiveness endpoint analysis will be conducted on the PP analysis set.

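### Section 4.4.1 lets a subject be terminated after the device attempt for a newly met exclusion criterion, so a later primary safety event can go unobserved and be imputed without regard to the complication behind the exit

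*Combined protocol and SAP*

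**What the plan says.** - **Termination (Section 4.4.1).** "A subject may be terminated if they meet an exclusion criterion (either newly developed or not previously recognized) that precludes further study participation". The wording is permissive. It covers criteria that arise after enrolment, and it does not say which criteria preclude participation.
- **Exclusion list (Section 4.2).** Criterion 1 is "Unstable neurological deficit (condition worsening within the last 90 days", criterion 2 is "Subarachnoid Hemorrhage within the last 60 days" and criterion 4 is "Modified Rankin Score (mRS) score ≥ 3". Criterion 9 is intolerance of, or contraindication to, aspirin or a P2Y12 inhibitor. Criterion 15 begins "Conditions that carry a high risk of neurological events or stroke (e.g., uncontrolled hypertension, prior ischemic stroke, Moya moyo disease".
- **Data handling (Section 4.4.2).** If a subject withdraws, "their data will be excluded from the data analysis from the time of withdrawal going forward". The next sentence adds: "All data collected prior to withdrawal will be included in the data analysis". The section heading names both withdrawal and termination, but the exclusion sentence speaks only of withdrawal.
- **Primary safety analysis (Section 10.3.4).** It uses the mITT set. A subject with no event and no completed 1-year follow-up is multiply imputed from demographic, procedural and aneurysm characteristics and from time since the procedure: "The longer that time period is, the less likely the subject will be imputed with an event". Success requires the upper limit of the two-sided 95% normal-approximation interval to lie below 15%.
- **Sensitivity analyses (Section 10.3.10).** These include scoring all missing endpoints as failures, and a tipping-point analysis.

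**The concern.** Applied after implantation, several eligibility criteria describe complications of the procedure. A minor stroke is not a primary event (Section 3.2.1), but an ischemic one literally creates the history named in criterion 15. An mRS of 3 or more is failure on the mRS 0–2 secondary endpoint. Subjects in these states plausibly carry above-average risk of a later major stroke or neurological death.

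If such a subject is terminated, no section requires follow-up to 1 year. The missing outcome is then filled from subjects who resemble this one at baseline and at the procedure, not from subjects who had the same complication. Missingness would depend on risk, while the decisive analysis treats it as explained by the listed inputs. In a single-arm trial judged against a fixed goal, no control arm offsets a downward bias.

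**Working it through.** **1. Passages side by side.** The clause sits badly with the rest of the protocol.

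| Section | What it implies for follow-up |
|---|---|
| 4.3 | An enrolled subject takes part for 5 years |
| 7.6 | A stroke or suspected stroke triggers work-up; exit is not mentioned |
| 7.11 | Every retreated subject stays in the study |
| 7.12 | If the whole study stops, subjects are followed to the 1-year visit for safety |
| 10.3.4 | Subjects with a failed implant are followed up to a year |
| 4.4.1 | A newly met exclusion criterion may end participation |

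Read literally, a retreated subject could also newly meet criterion 6 (two or more procedures on the target aneurysm), against Section 7.11. None of these sections expressly limits 4.4.1.

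**2. The plan's own figure.** Inputs from Section 10.2: goal 15%, anticipated rate 7%, 160 enrolled, 10% attrition, so n = 160 × 0.9 = 144. The continuity-corrected z test with null variance gives Φ[(0.08 − 1/288 − 1.96 × 0.02976) / 0.02126] = Φ(0.856) = 80.4%. This reproduces the stated 80% and confirms n = 144 as the planning number.

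**3. Pass mark of the planned rule.** Upper limit = p + 1.96 × √(p(1 − p)/n).

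| n | Passes | Fails |
|---|---|---|
| 144 | 14 events (14.56%) | 15 events (15.41%) |
| 160 | 16 events (14.65%) | 17 events (15.40%) |

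At the boundary, one unobserved event can change the result. With no event lost and a true rate of 15%, P(X ≤ 14 | n = 144) = 4.3%; P(X ≤ 16 | n = 160) is also 4.3%.

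**4. Effect of lost events.** The documents give neither the number of such terminations nor the later risk, so both are assumptions. Let f be the share of all true events that fall after a termination, and r the later risk in terminated subjects. The terminated share is t = 0.15f/r. If terminated subjects are imputed at the rate seen in the others, the expected estimate is 0.15(1 − f)/(1 − t). The false-pass chance is taken as P(X ≤ 14 | n = 144) at that rate.

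| f | r | t | Estimated rate | False pass |
|---|---|---|---|---|
| 0 | – | 0 | 15.0% | 4.3% |
| 10% | 20% | 7.5% | 14.6% | 5.7% |
| 10% | 30% | 5.0% | 14.2% | 7.2% |
| 10% | 40% | 3.75% | 14.0% | 8.1% |
| 10% | 100% | 1.5% | 13.7% | 9.8% |
| 20% | 20% | 15.0% | 14.1% | 7.7% |
| 20% | 30% | 10.0% | 13.3% | 12.2% |
| 20% | 40% | 7.5% | 13.0% | 14.9% |
| 20% | 100% | 3.0% | 12.4% | 20.3% |

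The r = 100% rows are upper cases: every terminated subject would have had an event. Some f = 20% rows need many terminations. At r = 20% it is 0.15 × 160 = 24 subjects, more than the plan's whole attrition allowance of 16; at r = 30% it is exactly 16.

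**5. Check by simulation.** 20,000 trials were run at n = 160 with 20 imputations and Rubin's rules, imputing from the observed rate without covariates or time. With 10% or 20% of event subjects terminated first, the chance of passing was 10.8% or 21.2%, close to the upper cases above. Scoring missing endpoints as failures held it at 4.1–4.5% in all scenarios run.

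**The case against.** The strongest reply is that the clause is narrower than it looks. It says a subject *may* be terminated, and only for a criterion that precludes participation; Section 4.2 addresses candidates. The sections tabulated above suggest that subjects with complications are meant to stay, and measuring mRS 0–2 out to 5 years makes little sense if a worse score ended participation. This stands as evidence of intent. It does not close the gap, because no section says which criteria preclude participation or limits the clause to the time before the device attempt.

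Other parts of the reply stand in full:

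- A reader might infer that strokes or hemorrhages can be erased from the count. They cannot: data before exit are kept, and an event that meets the definition makes the subject a failure.
- A reader might infer that terminated subjects leave the analysis set. The mITT set is defined by the attempt, so they remain and are imputed.
- A reader might fault the rule that longer follow-up lowers the imputed risk. In itself it is reasonable, since less time at risk remains.
- Section 10 describes itself as general and defers detail to a separate SAP. That the imputation omits the complication is true only of the inputs as stated here.
- Applying the data-exclusion sentence of Section 4.4.2 to termination is an interpretation. If it does not apply, the handling of terminated subjects is unspecified.

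The missing-as-failure and tipping-point analyses would make the problem visible. They are sensitivity analyses, and study success does not rest on them.

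**Conclusion.** The point holds in a limited form. The protocol gives discretion to end follow-up for reasons that can be complications of the procedure, and the primary safety analysis would fill the resulting gap without, as stated, using those reasons. The exposed sequence is specific: a sub-threshold complication, a discretionary termination, then a neurological death or major ipsilateral stroke before 1 year.

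The bias is downward whenever terminated subjects carry more risk than the imputation assigns them. Its size cannot be read from the documents. At a true 15% rate and n = 144, the false-pass chance goes from 4.3% to about 6–8% with 10% of events lost and about 8–15% with 20% lost, for an assumed later risk of 20–40%. A reader might take false-pass rates of about 10% and 20% as the expected effect. The documents do not support that, because those figures require every terminated subject to have gone on to an event. All these figures also rest on a simplified imputation at the observed rate.

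**What to change.** Reconcile Sections 4.2, 4.4.1, 4.4.2, 7.11 and 10.3.4 as follows:

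1. In Section 4.4.1, state that once the device has been attempted, meeting an exclusion criterion, whether newly developed or recognized late, is recorded as an AE or a deviation but does not by itself end study follow-up.
2. Where study visits or imaging stop for medical reasons, continue ascertainment of vital status, stroke and AEs, with CEC adjudication, to 1 year unless the subject withdraws consent. This leaves room for subjects who can no longer undergo the 1-year DSA.
3. In Section 4.4.2, state that the sentence excluding later data applies to withdrawal of consent only.

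The change concerns data collection, not treatment. It costs protocol wording and a few extra follow-up contacts. Outcomes not collected cannot be recovered at analysis.

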4.4.2. Handling of Participant Withdrawals or Termination

Subjects that withdraw consent after treatment are not required to undergo follow-up after withdrawal. They will not be replaced and will be considered part of the subject cohort. The reason for early withdrawal will be documented in the source documents and case report forms.

In the event a subject withdraws from the study, their data will be excluded from the data analysis from the time of withdrawal going forward. All data collected prior to withdrawal will be included in the data analysis.

5. Study Device

5.1. Study Device Description

5.1.1. Device Acquisition

The PulseRider investigational device is manufactured by Pulsar Vascular, Inc., in Los Gatos, California. The device will be provided to the clinical study sites by the Sponsor, Pulsar Vascular, Inc. after obtaining the fully executed clinical study agreement and IRB approval at each site.

5.1.2. Device Appearance, Packaging, and Labeling Description

The PulseRider Aneurysm Neck Reconstruction Device is a self-expanding nitinol implant designed to retain embolic coils within an aneurysm occurring at a vessel bifurcation. The PulseRider is comprised of the torque device, delivery wire, introducer, and implant.

There are three defining attributes of the implant: shape, arch width and parent vessel diameter. The PulseRider is available in T and Y shapes (see Figure 5.1.2A) with 8 mm and 10 mm wide arches. The anchor base is available in sizes to treat parent arteries from 2.0 mm to 4.5 mm. Depending on the size of the aneurysm neck and parent vessel, the appropriate size PulseRider implant must be chosen to ensure adequate stability and

anatomical fit. Figure 5.1.2B illustrates the implant placed in a vessel bifurcation supporting embolic coils.

Figure 5.1.2A. PulseRider T and Y Shapes

There are three defining attributes of the implant:
shape, arch width, and parent vessel diameter.

[figure not shown]
[figure not shown]

Figure 5.1.2B. Implant Placed at a Vessel Bifurcation and Retaining Embolic Coils

The PulseRider device shall be placed according to the IDE Instructions for Use (IFU) using standard endovascular techniques. The IFU is packaged with each investigational device. The unique open cell frame configuration conforms to the vessel walls with a profoundly patent lumen profile. The device is retrievable and may be repositioned by retracting into the microcatheter at any time during or after deployment, but prior to detachment. The implant is deployed at the parent vessel bifurcation and across the aneurysm neck to provide a supporting framework, bridging the aneurysm neck while retaining embolic agents within the aneurysm. Platinum and radiopaque markers are located at the proximal end, the middle, and the distal tips for fluoroscopic visualization during placement.

5.1.3. Device Training Requirements and Investigator Experience

In addition to the clinical protocol training, all investigators who will be performing procedures for this study will be required to undergo training via a device in-service, which includes detailed reviews of the PulseRider IFU and device (specifications, indications for use, procedural components, etc.) as well as benchtop training under fluoroscopy. A proctored first case or prior human case experience is required. The combination of the didactic and hands-on portions of the device training will document and provide the investigator with the experience necessary to perform the protocol specified procedures for the study.

PulseRider should only be used by investigators who have received appropriate training in interventional neuroradiology and the treatment of intracranial aneurysms. Additionally, only the attending treating physicians who have completed device training will be able to perform the placement of the PulseRider and coils in the study procedure.

